5.1.4.3 Study Questionnaires

Study Questionnaires will be done by the patient and the health care provider after administration of the study drug (intranasal ketorolac [sprix]), prior to the patient leaving the clinical site. (See Appendix 2)

5.1.4.4. Standard-of-Care Procedures: Pain Management

Patients may receive additional medications as part of their emergency department treatment including additional pain medications, such as opioids. Any additional medications administered will be recorded. The need for additional medications (including the drug administered, the dose, the time, and the route of administration) will

be recorded. The need for additional pain medications (or the lack of need for additional pain medications) may also be a secondary efficacy endpoint.

5.1.5 Description and Documentation of Study Procedures

5.1.5.1 Study Number

The subject will be assigned a study number. This will be recorded in a study log. This will maintain patient confidentiality and eliminate patient identifiers from the patient case report form.

5.1.5.2 Demographics

The subject's age, gender, race/ethnicity, will be recorded.

5.1.5.3 Medical History

Relevant medical history for each subject will be obtained in order to determine eligibility in the study. Eligibility will be noted.

5.1.5.3 Medications during the Study

All medications administered in the emergency department (drug name, dose, route and time of administration) including the study drug and additional pain medications will be recorded.

5.1.5.4 Intranasal Ketorolac (Sprix) Administration during the Study

Intranasal Ketorolac (Sprix) will be administered in the standard manner as per the protocol and manufacturer instructions.

5.1.6 Efficacy Assessments

5.1.6.1 Pain Assessments

Pain scores will be recorded and documented before administration of the intranasal ketorolac (sprix) for a baseline pain assessment and at specified intervals after the administration of intranasal ketorolac (sprix). Post-treatment pain scores will be recorded immediately prior to discharge from the ED and immediately prior to any rescue (e.g. pain or sedative) medication. Post treatment pain scores will be collected for as long as the patient is in the clinical site and will be at 20 minutes, 40 minutes, 1 hour and for 1 hour intervals post treatment up to 6 hours (e.g. at 1, 2, 3, 4, 5, and 6 hours) in addition to pain scores immediately prior to rescue medication and immediately prior to discharge from the ED. Pain assessments will be by the Numeric Rating Scale (NRS).where 0 = no pain and 100 = the worst pain imaginable. (See Appendix 1)

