5.1.4.2 Study Pain Assessments

Study pain assessments will be done before and after the administration of the single dose of intranasal ketorolac (sprix). All patients will have a minimum of two pain scores (NRS): a baseline (pre administration of the intranasal ketorolac) and a post administration of intranasal ketorolac. The time that the pain score is done, whether at baseline or post intranasal administration of the ketorolac, will be recorded any time a baseline or post-treatment NRS pain score is done. A post-treatment NRS pain score will be done immediately prior to the patient leaving the ED and immediately prior to the patient receiving rescue medication (e.g. any additional pain medication or sedatives) with the time post-treatment to be recorded. Depending on the length of time the patient is in the ED, additional NRS pain scores will be done, if possible. While the patient is in the ED, additional NRS pain scores will be recorded at specified times after study drug administration; specifically, at 20 minutes, 40 minutes, 1 hour, 2 hours, 3 hours, 4 hours, 5 hours and 6 hours for as long as the patient remains in the clinical site, in addition to time 0 (baseline = before administration of the study drug). (See Appendix 1) The pain scores will be compared and analyzed for statistical significance comparing the baseline (pre-study drug administration) with the "post-study drug administration or "treatment" pain scores.

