7.2 Efficacy

The pain scores pre and post-treatment (after administration of the intranasal ketorolac [sprix]) will be compared. Pain scales are a continuous variable. Therefore, pain scales and other pain assessments (such as PID, SPID) (all continuous variables) will be compared using t-test or F-test.

The questionnaires (patient and health care provider) are discrete variables and will be compared using chi-square or Fischer's exact test.

Significance is at $p=0.05$.

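### The primary pre/post NRS comparison names no time point and does not exclude scores taken after rescue, so rescue relief could be counted as ketorolac effect in this one-arm trial

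*Combined protocol and SAP*

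**What the plan says.** **Analysis.** Section 7.2 says: "The pain scores pre and post-treatment (after administration of the intranasal ketorolac [sprix]) will be compared". It allows a t-test or an F-test at p=0.05. The last sentence of section 5.1.4.2 says much the same, beginning "The pain scores will be compared and analyzed for statistical significance comparing the baseline (pre-study drug administration". Sections 2.2.1 and 6.2.1 define the primary variable only as pain, or NRS, after dosing. Section 7.1 bases the sample size on mean PID differing from zero. None of these names a post-dose time.

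**Collection.** Sections 5.1.4.2 and 5.1.6.1 schedule eight post-dose scores, at 20 and 40 minutes and at 1, 2, 3, 4, 5 and 6 hours, while the patient is in the ED. Section 5.1.6.1 adds: "Post treatment pain scores will be collected for as long as the patient is in the clinical site". Collection does not stop at rescue. Section 5.1.4.2 also requires two event-driven scores: "A post-treatment NRS pain score will be done immediately prior to the patient leaving the ED", and one "immediately prior to the patient receiving rescue medication".

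**Rescue.** Section 5.1.4.4 says: "Patients may receive additional medications as part of their emergency department treatment including additional pain medications, such as opioids". Drug, dose, route and time are recorded under sections 5.1.4.4 and 5.1.5.3. Rescue has only a tentative place in the analysis: the need for additional pain drugs "or the lack of need for additional pain medications) may also be a secondary efficacy endpoint".

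Figure 1 and the content of Appendix 1A are not visible, so a time point shown only there cannot be ruled out.

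**The concern.** Two choices in the primary test are left open: which post-dose score is used, and whether it may follow another analgesic. For a rescued patient, the score taken on leaving the ED always follows rescue, and any later scheduled score does too. Both are post-treatment scores in the sense of section 7.2.

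In a randomised trial, a control arm would offset part of the relief from rescue drugs. Here there is none, and any fall in pain counts against the null value of zero. An analyst who follows section 7.2 to the letter could therefore credit an opioid's effect to ketorolac. With eight scheduled times and none named, the comparison could also be chosen once the results are known.

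**Working it through.** **1. The plan's own figure.** Section 7.1 gives n = 25, effect size 0.56 (mean PID / SD) and 80% power. With a two-sided 5% test and the normal approximation, n = ((1.960 + 0.842)/0.56)² = 25.03, and power at n = 25 is 79.96%. The stated figure reproduces. The exact t-test gives 76.6%. The calculation does not depend on the time point or on rescue, so the gap is in the analysis rule and not in the sample size.

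**2. Conventions.** Below, PID is baseline minus post-treatment, so relief is positive. This reverses the sign in section 7.1. Units are SDs of PID. A two-sided 5% t-test is assumed, because section 7.1 speaks of a difference from zero and section 7.2 states no sides.

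**3. Threshold.** The smallest significant observed mean PID is t(0.975, 24)/√25 = 2.064/5 = 0.41 SD. If the test were one-sided, it would be 1.711/5 = 0.34 SD.

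**4. Rescue contamination (illustration).** The documents give no rescue rate or rescue effect, so both are assumed. There is no ketorolac effect and no natural recovery. PID ~ N(0, 1), plus d with probability p, where p is the share rescued before the analysed score. The shift in mean PID is p × d, from 0.1 × 0.4 = 0.04 to 0.5 × 1.0 = 0.50 SD, against the design effect of 0.56. The chance of a significant result in ketorolac's favour (200,000 simulated trials per cell, n = 25) is:

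| Share rescued p | d = 0.4 SD | d = 1.0 SD |
|---|---|---|
| 0 | 2.5% | 2.5% |
| 10% | 4% | 6% |
| 20% | 6% | 14% |
| 30% | 8% | 25% |
| 50% | 16% | 57% |

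**5. Choice of time point (illustration).** Assume no effect, no rescue and no recovery, and that all 25 patients have all eight scores. The best of eight separate t-tests then gives a false benefit in 13%, 10% or 6% of trials at an assumed equal correlation between times of 0.5, 0.7 or 0.9.

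**6. What a pre-rescue rule can and cannot do.** With natural recovery of r SD and no rescue, a false benefit already occurs in 16% (r = 0.2), 30% (r = 0.3) or 67% (r = 0.5) of trials. Using the pre-rescue score returns these rates only if that score has the same mean change r. It may not, because it can be taken before recovery. With r = 0.5, 50% rescued and mean pre-rescue PID of 0, mean PID is 0.5 × 0.5 + 0.5 × 0 = 0.25 SD and the rate is about 21%, against 67% without rescue.

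**The case against.** The strongest reply is that the plan already protects itself. It requires a timed score before rescue, which suggests an intent to isolate ketorolac, and it records every drug and time. That stands as far as it goes: the gap can be repaired from planned data. It does not close the gap, because no visible analysis passage gives that score precedence.

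A reader might infer that the plan deliberately puts post-rescue scores into the primary test. The documents do not say so. Section 5.1.6.1 only lists when scores are collected, and collecting them after rescue is no error. What can be said is that sections 5.1.4.2 and 7.2 do not exclude them.

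Section 7.2 also allows an F-test. One joint test over time would avoid picking a time point, so the best-of-eight figure applies only to separate t-tests. It would not remove rescue contamination. That figure is also an idealisation, since section 5.1.4.2 asks for additional scores only if possible.

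A further objection is that the missing control arm matters more: recovery of 0.5 SD alone gives 67%. That is correct, and the change proposed here does not address it. Rescue relief is the part that an analysis rule can address with the data in hand.

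Finally, carrying a pre-rescue score forward is one defensible strategy among several, and leaving the ED is a different event from being rescued. That also stands, and is why sensitivity analyses belong with the rule.

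**Conclusion.** The concern holds in this form: the primary comparison has no named time point and no rule against post-rescue scores, so relief from rescue drugs could be counted as ketorolac effect and the time point could be chosen late.

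The size cannot be fixed from the documents. Under the assumptions in the working (no ketorolac effect, no natural recovery, two-sided test, 10% to 50% rescued, drop of 0.4 to 1.0 SD), the false-benefit rate is 4% to 57% instead of 2.5%. Selecting among eight complete time points gives 6% to 13% by itself.

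Two stronger readings should be resisted. These percentages are not estimates for this trial, since its rescue rate and effect are unknown. Nor would a rescue rule make the test a clean test of ketorolac: natural recovery, placebo response and regression to the mean (entry requires NRS of at least 40 out of 100) all remain, and the no-rescue error rate returns only if pre-rescue scores show the same mean change.

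**What to change.** State in section 7.2, before analysis:

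1. One primary post-dose time point from the existing schedule, chosen and justified by the sponsor. The background's third-molar trial reports 21.5 minutes to perceptible and 66 minutes to meaningful relief. Test the NRS change there by one paired t-test, with the sign of PID stated once and used consistently with section 7.1.
2. No score taken after rescue enters the primary analysis. Patients rescued before the time point contribute their recorded pre-rescue NRS. Patients who leave earlier without rescue contribute their pre-departure NRS.
3. Two sensitivity analyses: post-rescue scores as observed, and change set to 0 for patients rescued before the time point.
4. Other time points shown descriptively, with the numbers still in the ED and the numbers rescued.

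A lesser point: state one fixed SPID window in Appendix 1D with the same rule, since its length could otherwise vary with ED stay. A short window loses comparability with the cited 4-, 6- and 8-hour results, and a long one needs more carried-forward scores.

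The cost is SAP wording and minor programming. The scores and drug times are already required, rescue care is unchanged, and no patient is lost to the analysis because of rescue. The real downside is that an early pre-rescue score can bias the estimate downward, possibly substantially, and more so with a later time point. The sensitivity analyses show the range.

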5.1.6.2. Patient Questionnaires

Patient questionnaires will be obtained after administration of the intranasal ketorolac (sprix) and prior to the patient leaving the clinical site. (See Appendix 2)

5.1.6.3 Health Care Provider's Questionnaire(s)

The health care provider questionnaires will be obtained after administration of the intranasal ketorolac (sprix) and prior to the patient leaving the clinical site. (See Appendix 2)

5.1.6.4 Safety Assessments

5.1.6.5 Site Assessments: Clinical

Site assessments (clinical) of the nasal passageways e.g. an examination of both nostrils) will be done before and after administration of the intranasal ketorolac (sprix). This will document that there is no changes in the nasal mucosa, etc. secondary to the administration of the intranasal drug (sprix).

5.1.6.6 Side Effects/Adverse Events

Any and all side effects/adverse effects will be documented on the case report form. The health care provider will determine whether the side effect/adverse event is or is not related to the intranasal ketorolac (sprix).

5.2 Protocol Deviations

No deviations to the inclusion/exclusion criteria are allowed in this study. All deviations will be recorded on the patient's chart and on the appropriate case report form.

5.3 Study Withdrawal Criteria

5.4 Discontinuation of Study Treatment/Early Release from the Study

A subject who is enrolled in the study and for whom study treatment is prematurely terminated will be considered to be discontinued from study treatment. After discontinuation/early release from the study, the subject will receive standard-of-care treatment as per the treating clinician. End of Study Efficacy and Safety assessments will be performed, if appropriate and whenever possible.

5.5 Withdrawal for the Study

A subject may be withdrawn from the study at any time for any reason and without penalty or prejudice. The following situations may be cause for a subject to be withdrawn from the study:

- Subject did not fulfill the inclusion or exclusion criteria.
- Subject experienced a significant complication, deemed due to the study treatment
- Subject developed an intercurrent illness, condition, or procedural complication that would interfere with continued participation
- Subject voluntarily withdrew consent/ authorization
- Subject was in violation of the protocol
- Treating health care provider (e.g. physician or mid-level provider) deemed it in the best medical interest of the subject to terminate involvement in the study at any time

Upon occurrence of a serious adverse event or intolerable adverse event, the principal investigator will be notified. If a subject is discontinued from study treatment due to a serious adverse event, the event will be followed until resolution. The investigational staff will record on the case report form the reason(s) for discontinuation.

5.6 Noncompliance/Replacement

Subjects who discontinue from the study prematurely will not be replaced.

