7. DATA ANALYSIS AND STATISTICAL METHODOLOGY

7.1 Planned Sample Size

Since this is a prospective, efficacy and safety trial, the planned enrollment is for 25 patients who will receive a single dose of intranasal ketorolac. This sample size provides 80% power to demonstrate that the mean pain intensity to demonstrate that the mean pain intensity difference (PID), (where the PID = post-treatment NRS – baseline NRS) differs from zero when the effect size is 0.56. The effect size was calculated as the mean PID divided by the standard deviation.

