8. TERMINATION OF THE STUDY

The study will be terminated when 25 subjects are enrolled and all data is obtained and documented on the case report form. A statistical analysis will follow, an abstract for presentation will be submitted and a manuscript for publication in a peer reviewed medical journal will be written.

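### The 80% power in 7.1 belongs to 25 dosed patients with no reserve, but enrolment stops at 25 enrolled and leavers are not replaced, so each subject lost before dosing lowers the stated size and power.

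*Combined protocol and SAP*

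**What the plan says.** Four places in the combined protocol and SAP bear on this.

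- **7.1 Planned Sample Size:** "the planned enrollment is for 25 patients who will receive a single dose of intranasal ketorolac". The next sentence begins "This sample size provides 80% power", and the target is that the mean PID "differs from zero when the effect size is 0.56". The effect size is standardised: "The effect size was calculated as the mean PID divided by the standard deviation". No allowance for loss is made.
- **8. Termination of the Study:** "The study will be terminated when 25 subjects are enrolled". The same sentence adds that the data must be complete on the case report form. It does not say that 25 patients must be dosed or evaluable.
- **5.5 Withdrawal:** "A subject may be withdrawn from the study at any time for any reason". The listed grounds include failing the entry criteria, withdrawing consent and violating the protocol, all of which can arise before the dose.
- **5.6 Noncompliance/Replacement:** "Subjects who discontinue from the study prematurely will not be replaced".

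The documents define no analysis set, missing-data rule or expected loss rate.

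**The concern.** The power statement counts one thing and the stopping rule counts another. Section 7.1 describes patients who are dosed; section 8 counts patients who are enrolled. Under 5.5 a subject can be enrolled and then leave before the spray is given, and 5.6 bars filling that place. The number enrolled is therefore a ceiling on the number analysed, while 7.1 needs that ceiling to be reached exactly.

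At stake is whether the trial delivers the size and power it states. This sentence in 7.1 is the only justification given for the sample size, and with 25 places each one counts.

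**Working it through.** **Inputs.** n = 25, power 80% and effect size d = 0.56 (mean PID / SD of PID) are from 7.1. The significance level 0.05 and the t-test are from 7.2. Sidedness is not stated; I take two-sided because 7.1 tests for a difference from zero in either direction.

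**Step 1: reproduce the plan's figure.** For a one-sample test of mean PID = 0, the normal approximation gives

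n = ((1.96 + 0.8416) / 0.56)² = 25.03.

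Power at n = 25 is Φ(0.56 × √25 − 1.96) = Φ(0.84) = 79.96%. This matches the stated 80%, with no patient to spare. One-sided versions do not match: the normal approximation would need only 20 patients, and the t-test would give 85.9% at 25. Section 7.1 names no formula, so the two-sided normal approximation is inferred from the match.

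**Step 2: the planned test.** For the two-sided t-test, power is the probability that a noncentral t variable with n − 1 degrees of freedom and noncentrality 0.56√n falls outside ± t(0.975, n − 1).

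**Step 3: power by number analysed, d = 0.56.**

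| Analysed | Normal approximation | Two-sided t-test | Effect size detectable with 80% power (t-test) |
|---|---|---|---|
| 25 | 80.0% | 76.6% | 0.584 |
| 24 | 78.3% | 74.8% | 0.597 |
| 23 | 76.6% | 72.8% | 0.611 |
| 22 | 74.8% | 70.7% | 0.626 |

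On either basis, each of the first three losses costs about 2 points (1.7 to 2.1).

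**Step 4: which exits cost a PID.** A PID needs one baseline and one post-dose NRS.

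- *Before dosing:* no post-dose score can exist. The place is used under section 8 and cannot be refilled under 5.6.
- *After dosing:* 5.1.4.2 expects every patient to have at least two scores. It and 5.1.6.1 require a score just before rescue medication and another just before departure. Section 5.4 asks for final assessments after early release where feasible. Most such patients should still yield a PID.

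**Step 5: how likely is a full 25?** The documents give no rate. If each patient independently had an assumed chance p of yielding no PID, the chance that all 25 are analysed is (1 − p)²⁵: 60% at p = 0.02, 28% at p = 0.05 and 7% at p = 0.10. These figures only illustrate how strongly the answer depends on p.

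**The case against.** The strongest reply is that withdrawal from the study is not loss from the analysis. Treatment is a single dose, given and assessed in one emergency visit. Nothing in 5.4 to 5.6 removes withdrawn subjects from the efficacy analysis, and the required post-dose scores protect the PID. This stands for dosed patients. A reader might infer from 5.5 that every listed ground for withdrawal costs a data point; the documents do not support that, since several grounds can arise after a PID exists and a treatment complication can arise only after dosing.

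A reader might also infer that the trial will usually analyse fewer than 25. That too is unsupported: no loss rate is given, and at an assumed 2% a full 25 is more likely than not.

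It can be added that the window before dosing is short, that 4.2 places identification, consent and baseline scores ahead of the dose, that 5.2 allows no eligibility deviations, and that a consented patient who fails screening need not count as enrolled. This narrows the exposure without closing it. Enrolment is not defined as dosing, and 5.5 itself foresees withdrawing a subject who proves not to meet the entry criteria. Section 8's requirement for complete data does not restore a lost place.

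Finally, barring replacement is a legitimate design choice, and one loss costs under two points. Both are true. The bar is sound after dosing, where replacement could select on response in an unblinded, uncontrolled study. It protects nothing before dosing, when no response has been seen.

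**Conclusion.** The point holds in a limited form. Section 7.1 needs 25 dosed and analysed patients for its stated power, and sections 5.5, 5.6 and 8 together do not secure 25 dosed patients. Each subject lost before dosing takes the trial below its stated size and lowers power by about 2 points. Three losses would leave 74.8% on the approximation that reproduces 7.1, or 70.7% under the planned t-test.

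This rests on d = 0.56, a two-sided 0.05 level, and enrolment being counted before the dose.

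Two stronger readings should be resisted. The shortfall does not make the trial invalid; it is small per patient and its likelihood is unknown. Nor should one conclude that 80% is secure once all 25 are analysed: under the t-test in 7.2 the figure is 76.6% even with no loss, so any corrected text should use the t-test figures.

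**What to change.** - **5.6 and 8:** count the 25 as patients dosed. Allow replacement of a subject who leaves after enrolment but before dosing, and keep the bar on replacement after dosing.
- **7.2:** state that every dosed patient with a baseline and a post-dose NRS is analysed, including those later withdrawn under 5.5.
- **7.1:** restate the power for the two-sided t-test at effect size 0.56: 76.6% if all 25 are analysed, 74.8% at 24, 72.8% at 23 and 70.7% at 22.

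Replacement before dosing cannot select on pain response, and planned doses stay at 25. The cost is a few words in four sections, a slightly less favourable stated power and possibly a few more consents. The change secures 25 dosed patients but does not restore 80% under the t-test. That would take 27 (79.98%) to 28 (81.5%) analysed patients, which is a separate decision for the sponsor.
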